7.3 HANDLING OF MISSING DATA

For primary efficacy endpoint and other endpoints which are continuous in nature, the use of a restricted maximum likelihood (REML)-based mixed model repeated measures (MMRM) approach, if feasible, will ensure that missing data are handled implicitly, via a missing at random assumption, by the statistical model.

For efficacy endpoints which are binary nature, a Non Response Imputation (NRI) approach will be applied to the missing visits up to Week 12; that is, imputing as a failure to achieve a response in the visits with missing endpoint score, however:

- If there are available data at the visits both before and after the visit with a missing outcome, then impute as a success only if both the preceding and the following measurement indicate success and no rescue medication has been given during this period.
- Otherwise, impute as a failure to achieve a response (i.e. no response imputation)

NRI is a conservative imputation scheme because it assumes that use of rescue therapy or missing data due to any other reason is related to treatment failure. In addition, for secondary binary endpoint, HiSCR at Week 12, multiple imputation based method will be applied as sensitivity analysis.

Further sensitivity analyses to assess the robustness of the results on efficacy endpoint will be described in the TSAP if necessary.

With respect to safety evaluations, it is not planned to impute missing values.

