5.2.2 Secondary endpoint(s)

[figure not shown]
Secondary Endpoints at Week 12 are defined as described below:

[figure not shown]
- Percent change from baseline in draining fistula count at Week 12
(Only patients with at least one draining fistula at baseline will be used for analysis).
- Achievement of Hidradenitis Suppurativa Clinical Response (HiSCR) at Week 12. HiSCR is defined as at least a 50% reduction in the total AN count with no increase in abscess count and no increase in draining fistula count relative to baseline.
- Absolute change from baseline in International Hidradenitis Suppurativa Severity Score System (IHS4) value at Week 12
- Absolute change from baseline in HASI score at Week 12
- Achievement of PGA score of 0 or 1 at Week 12
- Achievement of at least 30% reduction from baseline in Numerical rating scale (NRS30) in Patient's Global Assessment of HS Pain at Week 12
- Occurrence of complete elimination of draining fistulas at Week 12
(Only patients with at least one draining fistula at baseline will be used for analysis).
- Occurrence of at least one flare (defined as at least 25 % increase in AN count with a minimum increase of 2 relative to baseline) up to Week 12
- Absolute change from baseline in DLQI Score at Week 12
- Absolute change from baseline in HiS-QoL Total Score at Week 12

[figure not shown]
See [Section 10.1](#) for further details regarding endpoint definition and derivation.

The following safety endpoint is also defined:

- The occurrence of Treatment Emergent Adverse Events (TEAEs)

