6.6.2 Efficacy data

Based on the different reasons for patients' data missing for different endpoints, various approaches will be used to assess the impact of missing data on the efficacy endpoints of this trial, depending upon the type of the endpoint (cf. [Table 6.3: 1](#)). Approaches to be applied are described below.

Proprietary confidential information © 2021 Boehringer Ingelheim International GmbH or one or more of its affiliated companies
Missing data imputations will be performed using all available on-treatment data observed up to the respective analysis cut-off date, if applicable.

Some efficacy endpoints are defined with a particular binary outcome, i.e. Achievement of PGA score of 0 or 1. Then imputation is planned to take place only at the binary level, i.e., the PGA score itself as a ordinal variable will not be imputed, but the binary endpoints derived based on these scores will be imputed, unless otherwise specified.

Continuous efficacy endpoints

For efficacy endpoints which are continuous in nature, the use of a restricted maximum likelihood (REML)-based mixed effect model with repeated measures (MMRM) approach, if applicable, will ensure that missing data are handled implicitly, via a missing at random assumption, by the statistical model.

In addition, the efficacy endpoints during randomized treatment period may be displayed descriptively using following methods:

- Observed cases (OC) approach will include all collected data, without imputation for any missing data. Such an OC approach will exclude all values measured after intake of a rescue therapy.
- Observed cases (OC-IR) approach will include all collected data, without imputation for any missing data. Such approach will be used as a sensitivity method for data display and is an extension of the OC approach which includes additionally all values which were measured after rescue therapy. Will also include all values measured after any use of investigator prescribed SoC.

Binary efficacy endpoints

Primary Imputation Approach – No Response Imputation [NRI]:

For all binary endpoints (i.e. endpoints that are either 1 (patient responded) or 0 (patient did not respond)), the following will be performed as the primary imputation approach (analysis type):

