- If there are data at visits both before and after the visit with a missing outcome, then impute as success only if both neighbouring visits also represent a success (independent of whether the preceding and following observations were selected for analysis based on time windows described in [Section 6.7](#) and no rescue treatment has been given during this period).
- Otherwise, impute as a failure.

Other Imputation Approaches:

- OC method will be also used to display the binary data.
- Multiple Imputation (MI) approach:
For selected secondary binary endpoint, i.e., achievement of HiSCR at Week 12, multiple imputation (MI) will be used to handle missing data as a sensitivity analysis. Use baseline and on-treatment data only and impute HiSCR as binary variables with values 0, 1. The

Proprietary confidential information © 2021 Boehringer Ingelheim International GmbH or one or more of its affiliated companies
imputation will be done using OC data as the input dataset, and will follow the steps outlined below:

1. *Multiple Imputation of Missing data:* use SAS procedure PROC MI with the Fully Conditional Specification (FCS) method and corresponding options/statements (SAS manual). Discriminant function method is used to impute missing values by using the ordering of the class level in each variable.

```
PROC MI DATA= hiscr_mi2 seed= 136852 nimpute=100 out=mi_fcs;  
CLASS HiSCR_base- HiSCR_12 trt stratum;  
VAR HiSCR_base- HiSCR_12 trt stratum;  
FCS DISCRIM (HiSCR_base- HiSCR_12 trt stratum /CLASSEFFECTS=include);  
RUN;
```

Note that the seed 136852 will be used throughout. If a second seed is required, 136853 will be used, and so on as necessary.

2. *Analysis of Completed Datasets:* The imputed complete dataset will be used to calculate the response rate for each arm. The risk difference will be also calculated together with the standard error based on the normal approximation.
3. *Combine Results:* Separate approach will be applied to the combination of the response rate for each arm and the difference between them.
 - For the response rate of each arm, the distributions are not expected to be approximately normal, so Rubin's rules (13) should not be used. Instead, the point estimate will be calculated as the mean of individual imputations and the 95% confidence interval for each arm will implement the MIWilson(14) approach.

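### The HiSCR multiple imputation fills in post-rescue visits without the AN count that triggers rescue, so it overstates response in rescued patients

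*SAP*

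**What the plan says.** **Main analysis.** Protocol 7.2.3 and SAP 7.5.2 censor binary data after rescue and then apply NRI. NRI allows a success only when both neighbouring visits are successes and no rescue was given in between. SAP 6.6.2 then says: "Otherwise, impute as a failure". Protocol 7.3 calls the method conservative because "it assumes that use of rescue therapy or missing data due to any other reason is related to treatment failure".

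**Sensitivity analysis.** For HiSCR at Week 12, SAP 6.6.2 plans multiple imputation (MI), shown as EC-H-MI in Table 6.3:1. The "imputation will be done using OC data as the input dataset", and the same section defines OC: "Such an OC approach will exclude all values measured after intake of a rescue therapy". The instruction is to "impute HiSCR as binary variables with values 0, 1". The variable list in the code is "VAR HiSCR_base- HiSCR_12 trt stratum". It contains no rescue indicator, no lesion count and no departure term.

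**Trigger and data.** Protocol 4.2.2.2 defines disease worsening as an AN count 150% above baseline. The flowchart schedules AN, abscess and draining fistula counts at every visit to Week 12.

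**The concern.** Rescue is given because the AN count has risen steeply. That count is in the database, but the imputation never sees it. On the 0/1 scale, a patient at 2.5 times baseline and a patient with a 45% reduction are both 0. If their earlier 0/1 history, arm and stratum agree, they get the same imputed probability of response at Week 12.

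The SAP does not write missing at random for this step, but it is what fully conditional specification with no departure term assumes. The reason for the gap (rescue) depends on a variable that predicts the outcome and is outside the model, so the assumption is hard to defend even for the effect in the absence of rescue.

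A second problem is interpretation. MI differs from NRI in two ways at once: rescue goes from failure to imputed, and other missing data go from failure to imputed. A gap between the two results cannot be assigned to either change.

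**Working it through.** The documents give no figure for this analysis, so there is none to reproduce. The planning inputs used below come from Protocol 7.5. Read as stated, they return its main figure: SE = 45 × √(1/30 + 1/15) = 14.23, and Φ((42 − 30)/14.23) = 80.05%, against 80.1% in Table 7.5:1.

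**Step 1. A rescued patient under each method.** Week 12 is the last scheduled HiSCR visit and post-rescue values are censored, so the neighbouring-success exception cannot apply. A patient rescued before Week 12 has response probability 0 under NRI. Under MI the probability is whatever the model gives to patients with the same 0/1 history, arm and stratum.

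**Step 2. What leaving out the AN count does.** Assumptions: placebo AN ratio to baseline is lognormal with mean 0.80 and SD 0.45 (20% reduction, SD 45 points), held constant over visits, with autoregressive correlation. The correlation and the constant mean are not in the documents. Only the AN part of HiSCR is used.

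- σ² = ln(1 + (0.45/0.80)²) = 0.275, so σ = 0.524; μ = ln 0.80 − 0.137 = −0.361.
- P(ratio ≤ 0.5) = Φ((−0.693 + 0.361)/0.524) = 26%. This is close to the 26% to 28% placebo response in Protocol 1.1.

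Simulated chance (%) of at least a 50% AN reduction at Week 12, for patients with no such reduction up to Week 4 / 6 / 8 (2,000,000 trajectories per row):

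| Two-week correlation | All with history 0 (what the model sees) | Of these, AN ≥ 2.5 × baseline | Of these, AN 0.5 to 0.6 × baseline |
|---|---|---|---|
| 0.60 | 23.9 / 22.2 / 19.3 | 16.0 / 10.4 / 4.1 | 27.9 / 29.3 / 30.8 |
| 0.75 | 20.2 / 17.8 / 14.5 | 6.0 / 2.5 / 0.4 | 30.1 / 31.0 / 32.0 |
| 0.85 | 16.1 / 13.5 / 10.5 | 0.8 / 0.1 / 0.0 | 32.0 / 32.4 / 32.6 |
| 0.95 | 9.1 / 7.2 / 5.3 | 0.0 / 0.0 / 0.0 | 32.0 / 30.9 / 29.3 |

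The model gives the second column to patients who belong in the third.

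**Step 3. Size per rescued patient.** One patient switched to responder moves the arm rate by 1/15 = 6.7 points (placebo) or 1/30 = 3.3 points (spesolimab). At an imputed probability of 10% to 20%, one rescued placebo patient adds 0.7 to 1.3 points on average.

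**Step 4. How often.** P(ratio ≥ 2.5) = 1 − Φ((0.916 + 0.361)/0.524) = 0.7% per visit. Over Weeks 4, 6, 8 and 10, 1.4% to 2.6% ever reach it (correlation 0.95 to 0.60). That is 0.2 to 0.4 of 15 placebo patients; three or more of 15 has probability 0.1% to 0.6%. At correlation 0.75 the expected addition to the placebo rate is at most 0.0223 × 0.202 = 0.45 points.

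**Step 5. Direction.** An illustrative discriminant-function imputation was run with 30 and 15 patients, assumed HiSCR rates of 50% and 27%, and assumed rescue counts. Rescued patients were imputed as responders with average probability 11% to 47% on spesolimab and 7% to 26% on placebo. Relative to NRI, the risk difference moved by as much as −4.1 points (1 spesolimab and 3 placebo patients rescued) and +4.8 points (4 and 1 rescued).

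**The case against.** The best defence is the estimand. Protocol 2.1.1 and 7.2.2 aim at the effect without rescue, and SAP Table 6.3:1 labels both analyses EC-H: same censoring, different imputation. MI after censoring fits that aim, and forcing failure after rescue moves to a composite estimand. This stands as a defence of imputing past rescue. It does not defend leaving out the AN count, which the hypothetical estimand needs just as much.

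Binary-level imputation is also a declared convention of SAP 6.6.2, and modelling several counts over seven visits in 45 patients can be unstable. That is a fair reason for a small model, but not for one with no counts.

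Some stronger readings are tempting but not supported:

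- *The MI fails a purpose set by Protocol 7.3.* That section adds MI alongside NRI and states no narrower purpose.
- *It is the only robustness check on HiSCR.* The SAP also plans an OC display and a Bayesian analysis with historical placebo data (7.5.2).
- *It favours spesolimab.* Extra placebo responders shrink the apparent benefit; the net effect depends on which arm has more rescue.
- *It shifts the placebo rate by several points.* That needs about three rescued placebo patients, which is unlikely under the planning distribution.

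Finally, SAP 5.4.5 and 5.4.6, which hold the intercurrent-event rules, are not in the public text. A further rule on rescue there cannot be excluded.

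**Conclusion.** The concern holds for the imputation model. As written, it gives rescued patients of either arm a response probability that ignores the rise in AN count that led to rescue. With two-week correlations of 0.75 to 0.85 this is roughly 10% to 20% instead of 0% to 6%. The gap remains at 0.60 and 0.95, at different levels. These figures rest on the lognormal shape, the constant mean and the assumed correlations; the rescue counts and HiSCR rates behind the risk-difference range are also assumptions.

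The effect is per rescued patient, expected to be small in total, and of no fixed direction. It concerns one sensitivity analysis of a secondary endpoint in a trial without confirmatory testing, and the primary analysis is untouched. It rates as minor to moderate, and is worth correcting because the data needed are already collected.

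**What to change.** In SAP 6.6.2:

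1. Bring the counts into the imputation with a parsimonious model, for example baseline AN and fistula counts plus AN change at the last one or two observed visits before the gap. Alternatively, impute the counts and derive HiSCR from them.
2. Also run the MI with HiSCR set to 0 at all visits after rescue, so that only other missing data are imputed. A difference from NRI then reflects the missing-data assumption alone; the rescue-driven part is zero by construction.
3. Label any version that imputes past rescue as supplementary, targeting the hypothetical no-rescue estimand.
4. If SAP 5.4.5 or 5.4.6 already has a rule for this, refer to it here.

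Removing `HiSCR_base` is tidying only. HiSCR is defined by reduction from baseline ("HiSCR is defined as at least a 50% reduction in the total AN count"), so this variable is 0 for everyone.

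The cost is a few lines of SAP text and some code. The risk is unstable estimation with 45 patients, so a fallback with fewer predictors should be named in advance. No trial procedure changes, and the NRI analysis stays as planned.

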Trial endpoints	The primary endpoint is the percent change from baseline in total abscess and inflammatory nodule count at Week 12. Secondary endpoints are defined as described below: -Percent change from baseline in draining fistula count at Week 12 -Achievement of Hidradenitis Suppurativa Clinical Response (HiSCR) at Week 12.

	
-Absolute change from baseline in International Hidradenitis Suppurativa Severity Score System (IHS4) value at Week 12
 
-Absolute change from baseline in HASI score at Week 12
 
-Achievement of PGA score of 0 or 1 at Week 12
 
- Achievement of at least 30% reduction from baseline in Numerical rating scale (NRS30) in Patient's Global Assessment of HS Pain at Week 12
 
-Occurrence of complete elimination of draining fistulas at Week 12
 
-Occurrence of at least one flare (defined as at least 25 % increase in AN count with a minimum increase of 2 relative to baseline) up to Week 12.
 
-Absolute change from baseline in DLQI Score at Week 12.
 
-Absolute change from baseline in HiS-QoL Total Score at Week 12.
 
The following safety endpoint is also defined:
 
-The occurrence of Treatment Emergent Adverse Events (TEAEs)

Trial design	International, multi-center, placebo-controlled, double blind, randomized trial assessing the efficacy and safety of spesolimab versus placebo in patients with moderate to severe HS over 12 weeks
Total number of patients randomized	45
Number of patients on each treatment	30 active arm 15 placebo arm
Diagnosis	Hidradenitis suppurativa
Main in- and exclusion criteria	
Inclusion Criteria:
 
 • Male or female adult patients, 18 years of age or older • Have moderate to severe HS for at least 1 year prior to the baseline visit, as determined by the investigator • Have HS lesions in at least 2 distinct anatomic area • Has a total abscess and inflammatory nodule (AN) count of greater than or equal to 5. • Biologic naïve or TNFi-failure for HS • Total draining fistula count of less than or equal to 20 
Exclusion criteria:
 
 • Presence of active skin lesions other than HS that interferes with the assessment of HS.
Test product 1	Spesolimab
dose	1200mg weekly at Weeks 0, 1 and 2 for a total loading dose of 3600mg
mode of administration	intravenous (i.v.)
Test product 2	Spesolimab
dose	1200 mg every 2 weeks at Weeks 4, 6, 8 and 10
mode of administration	subcutaneous (s.c.)

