1.3 RATIONALE FOR PERFORMING THE TRIAL

Adalimumab (TNFi) is the only approved biologic for HS, with the response rate of 42%-59% versus placebo response of 26% – 28%, with a schedule of weekly subcutaneous dosing.

Long-term safety concerns are pertinent in the treatment of HS, where the dosing regimen of biologics is typically more intensive compared to other inflammatory diseases, such as psoriasis. Considering the above, a more efficacious and safer molecule with better dosing regimens is a substantial need in HS patients.

Spesolimab is an IL-36R antagonist currently in development for the treatment of GPP. HS and generalized pustular psoriasis (GPP) have similarity in neutrophil infiltration and pustules, with pustules in HS being subcutaneous. IL-36 alpha, beta and gamma mRNA expression are upregulated in lesional skin in HS patients with a decrease in IL-36RN expression [[R20-3047](#)]. Internal ISH staining of HS lesions also confirms the increased expression of ligands. IL-36 is thought to be a central upstream mediator of an inflammatory loop which further activates the keratinocytes, amplifying the secretion of chemokines that lead to infiltration of immune cells to the skin. Infiltrated DCs and monocytes can be activated by IL-36 (internal data and published) to potentiate the APC function of DCs and also lead to secretion of chemokines and cytokines that can recruit more immune cells including neutrophils. IL-36 is a potent activator of neutrophil infiltration and in the context of HS, neutrophils are shown to undergo netosis leading to secretion of AMPs and type I Interferons [[R20-3155](#)]. Based on the role of IL-36 driving TH17 and TH1 responses in GPP (published and our internal data) and from animal models of atopic dermatitis (AtD), the hypothesis is that IL-36 is also a key driver of TH17 responses in skin of HS patients.

Study 1368-0052 is proof-of-clinical-concept study in HS designed to assess the efficacy and safety of spesolimab in this patient population. The results from this trial will enable the design of the further development.

1.4 BENEFIT - RISK ASSESSMENT.

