7.4 RANDOMIZATION

BI will arrange for the randomization and the packaging and labelling of trial medication. The randomization list will be generated using a validated system, which involves a pseudorandom number generator so that the resulting treatment will be both reproducible and

nonpredictable. The block size will be documented in the Clinical Trial Report. Access to the codes will be controlled and documented.

Stratification of the randomization will be performed for TNFi-naive population versus TNFi-failure population. Approximately 33 patients from TNFi-naive population and 12 patients from TNFi-failure population are planned to be randomized. Once either subpopulation has recruited the planned number of patients, the screening of that subpopulation may be considered to be closed.

Within each stratum, patients will be randomized in a 2:1 randomization ratio to receive Sepsolimab vs placebo. The randomization will be done in blocks to achieve balanced allocation.

The process of randomization is done via an IRT.

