 - For the risk difference, the distribution is approximately normal, so Rubin's rules can be used. Accordingly, PROC MIANALYZE is used to combine the analysis results from step 2 and generate valid statistical inferences by accounting for the variability introduced by the MI process.

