7.5 SECONDARY ENDPOINT(S)

7.5.1 Key secondary endpoint(s)

This section is not applicable as no key secondary endpoint has been specified.

7.5.2 (Other) Secondary endpoint(s)

For each of the secondary endpoint described below, hybrid strategy will be used to handle intercurrent events which lead to data censoring as described for the primary endpoint.

Continuous secondary endpoints

The continuous secondary endpoints up to Week 12 will be analysed using a MMRM approach based upon the model specification as described for the primary endpoint.

Additionally, subgroup analysis will be performed for variables as described in [Section 6.4](#).

Binary secondary endpoints

The binary secondary endpoints will be evaluated descriptively by treatment arm via frequency tables (with 95% confidence interval based on the Wilson score for each group and based on the Chan and Zhang method for risk difference). As in the case of the primary estimand, any binary data collected after use of any rescue therapy will be censored and then imputed using the NRI method as described in CTP section 7.3 “Handling of Missing Data”.

Example SAS code for CI of proportion difference by Chan and Zhang method is as follows:

```
PROC FREQ DATA=data;  
<WHERE treat IN ('Treatment_1','Treatment_2') ;>  
TABLES treat*endpoint_bin / RELRISK RISKDIFF.  
EXACT RELRISK (METHOD=SCORE column=2) RISKDIFF (METHOD=SCORE  
column=2);  
RUN;
```

For selected binary endpoint, e.g., achievement of HiSCR at Week 12, following additional analyses are planned.

Logistic regression analysis

Proprietary confidential information © 2021 Boehringer Ingelheim International GmbH or one or more of its affiliated companies
The difference in the proportion of patients with a response between Spesolimab and placebo will be analysed using predictive margins in a binary logistic model via %Margins in SAS®. Fixed classification effects will include treatment and stratification factor (TNFi-naive population versus TNFi-failure population).

Example SAS code:

```
%Margins(data= data,  
class    = treat stratum,  
response = endpoint_bin,  
roptions = event='1',  
dist     = binomial,  
model    = treat stratum,  
margins  = treat,  
options  = cl diff)
```

Stratified risk difference

[figure not shown]
A Mantel-Haenszel type weighted average of differences will be implemented with corresponding Wald confidence intervals based on the variance formula provided by Sato.

[figure not shown]
Example SAS code:

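### The HiSCR risk-difference intervals after multiple imputation and in the stratified analysis use symmetric normal limits with 30 versus 15 patients; at borrowed adalimumab rates the nominal 95% limits cover about 92–94% and lean towards benefit (low impact)

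*SAP*

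**What the plan says.** The Protocol synopsis plans "30 active arm 15 placebo arm". Protocol 7.4 adds "Within each stratum, patients will be randomized in a 2:1 randomization ratio" and "Approximately 33 patients from TNFi-naive population and 12 patients from TNFi-failure population are planned to be randomized".

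For HiSCR at Week 12 the SAP produces several intervals for the treatment difference:

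- **Main analysis (SAP 7.5.2).** Missing and post-rescue data are handled by non-response imputation. Limits are Wilson for each arm and Chan-Zhang (exact) for the difference.
- **Multiple imputation, as a sensitivity analysis (SAP 6.6.2).** There are 100 imputations. In each completed dataset, "The risk difference will be also calculated together with the standard error based on the normal approximation". For pooling, the SAP separates arms from contrast. Of the arms it says "For the response rate of each arm, the distributions are not expected to be approximately normal", and it uses MI-Wilson limits. Of the contrast it says "For the risk difference, the distribution is approximately normal, so Rubin's rules can be used".
- **Stratified difference, as an additional analysis (SAP 7.5.2).** "A Mantel-Haenszel type weighted average of differences will be implemented with corresponding Wald confidence intervals based on the variance formula provided by Sato". The code requests `commonriskdiff(cl=mh)`.
- **Logistic model with predictive margins (SAP 7.5.2).** Not examined here.

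Neither document supports the normality statement with a sample-size argument or a coverage figure.

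**The concern.** The SAP avoids normal limits for each arm's rate and for the main risk difference. It then uses them for the imputed and the stratified risk difference, which come from the same small arms.

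With 15 placebo patients the weak spot is the estimated standard error. When few placebo patients respond by chance, the observed difference is large and the estimated variance is small at the same moment. With 4 of 15 responders the placebo variance term is 0.2667 × 0.7333 / 15 = 0.0130; with 2 of 15 it is 0.1333 × 0.8667 / 15 = 0.0077. A symmetric interval is therefore tightest when the difference is most exaggerated, and its lower limit ends up too high.

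At stake is whether a stated 95% lower limit on the HiSCR benefit deserves that label. The trial does no confirmatory testing, so readers will judge the evidence from estimates and intervals.

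**Working it through.** **The plan's own figure.** The documents state no coverage or operating characteristic for HiSCR. The one figure that can be reproduced is for the primary endpoint (Protocol 7.5), and it confirms the arm sizes: Phi((42 − 30) / (45 × sqrt(1/30 + 1/15))) = Phi(12 / 14.23) = 80.05%, against 80.1% stated.

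**Inputs.** Arms 30 and 15 (Protocol synopsis). Strata 33 and 12 at 2:1, hence 22:11 and 8:4 (Protocol 7.4). Response rates 42% or 59% versus 26% or 28% (adalimumab, Protocol 1.1 and 1.3). Using these as HiSCR rates here is an assumption. So is reading the normal-approximation standard error as the unpooled one.

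**Step 1: unstratified Wald, complete data.** Limits are d ± 1.96 × sqrt(p1(1−p1)/30 + p2(1−p2)/15). At 42% versus 26% the true standard error is sqrt(0.00812 + 0.01283) = 0.145. All 31 × 16 outcomes were enumerated with their binomial probabilities. The comparator is Newcombe: with Wilson arm limits (l1, u1) and (l2, u2), lower = d − sqrt((p1−l1)² + (u2−p2)²) and upper = d + sqrt((u1−p1)² + (p2−l2)²).

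| True rates | Wald coverage % | Lower limit above truth % | Upper limit below truth % | Mean length | Newcombe coverage % | Lower limit above truth % | Upper limit below truth % | Mean length |
|---|---|---|---|---|---|---|---|---|
| 42 v 26 | 93.53 | 4.47 | 1.99 | 0.549 | 94.68 | 1.92 | 3.40 | 0.522 |
| 42 v 28 | 92.55 | 4.76 | 2.69 | 0.558 | 94.66 | 2.02 | 3.32 | 0.527 |
| 59 v 26 | 93.53 | 4.49 | 1.98 | 0.549 | 94.59 | 2.02 | 3.39 | 0.518 |
| 59 v 28 | 92.10 | 5.30 | 2.60 | 0.557 | 94.71 | 1.50 | 3.79 | 0.523 |

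Across the continuous range 42–59% by 26–28%, Wald covers 92.0–93.7% (mean 93.0%). With no true difference (26% or 28% in both arms), the Wald interval lies wholly above zero in 4.1–4.3% of trials; Newcombe does so in 1.8–1.9%.

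**Step 2: stratified Mantel-Haenszel with Sato variance.** The weights are 22 × 11 / 33 = 7.33 and 8 × 4 / 12 = 2.67. Exact enumeration over both strata, with equal rates in the strata, gives 93.2%, 92.7%, 93.0% and 92.4% in the order of the table. Stratified Newcombe limits with the same weights give 94.9–95.3%.

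**Step 3: multiple imputation.** This was simulated with 100 imputations, 6,000 trials per setting, arm-specific imputation from an earlier visit's response, and Rubin's rules with t limits. At 5–20% missing (an assumed range), coverage is 92.3–93.7%, with simulation error of about 0.3 points. Imputation does not remove the shortfall. The Newcombe-type combination of the two MI-Wilson intervals covers about 95–96% in a simulation of the same kind and is slightly narrower on average. The imputation model was simpler than the PROC MI FCS discriminant specification in the SAP.

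**Step 4: one illustration.** Take 15/30 versus 4/15, so d = 0.233.

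- Wald: 0.233 ± 1.96 × 0.146 = −0.053 to 0.520, length 0.573.
- Wilson arm limits: 0.332–0.668 and 0.109–0.520.
- Newcombe lower: 0.233 − sqrt(0.168² + 0.253²) = −0.070.
- Newcombe upper: 0.233 + sqrt(0.168² + 0.158²) = 0.464, length about 0.535.

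The Newcombe interval is shorter and sits lower.

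**The case against.** The best case for leaving the plan alone is that little depends on these intervals. Protocol 7.1 rules out confirmatory testing. There are no key secondary endpoints. The 30-point benchmark in Protocol 7.5 concerns AN count, not HiSCR. The main HiSCR interval is already exact. A loss of 1 to 3 points of coverage in supporting intervals will not change the trial's conclusion. All of that stands, and it sets the grade.

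Four stronger readings are tempting, and the documents do not support them:

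- **That the intervals are too short.** They are longer on average than the replacement (about 0.55–0.56 versus 0.52–0.53 unstratified). They are misplaced.
- **That the SAP contradicts itself by calling the arms non-normal and the difference normal.** A difference can be closer to normal than its parts. At these rates its skewness is only −0.12 to −0.14. The shortfall comes from the estimated standard error in small arms.
- **That the change would make the imputed and main results directly comparable.** Newcombe-type limits would still stand beside exact Chan-Zhang limits. The analyses also differ by design, in missing-data handling or in stratification.
- **That 92–94% is a property of this trial.** It depends on rates borrowed from another drug, while this trial also enrols TNFi failures. With placebo response near 15%, coverage is about 91–93%. Over active 30–70% and placebo 10–40%, Wald covers 91.1–94.5%.

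The replacement is not perfectly balanced either. Newcombe misses more often on the upper side (3.3–3.8%) than on the lower (1.5–2.0%), so its residual error is cautious about benefit.

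**Conclusion.** The point holds at low impact. Under the assumed adalimumab rates, the symmetric limits planned for the imputed and stratified HiSCR differences cover about 92–94% instead of 95%. On complete data nearly all of the excess error is a lower limit that is too high: 4.5–5.3% unstratified, against a nominal 2.5%.

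The complete-data and stratified figures are exact for the stated rates and strata. The multiple-imputation figure comes from a simplified simulation and is less firm. One sensitivity analysis and one additional analysis of a single secondary endpoint are affected. The primary endpoint and the main HiSCR interval are not.

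**What to change.** 1. **SAP 6.6.2, combining results for the risk difference.** Keep the pooled point estimate. Replace the Rubin/Wald limits with a Newcombe-type (MOVER) interval from the two MI-Wilson arm intervals already planned: lower = d − sqrt((p1−l1)² + (u2−p2)²), upper = d + sqrt((u1−p1)² + (p2−l2)²). Drop the sentence that rests the choice on approximate normality.
2. **SAP 7.5.2, stratified risk difference.** Keep the Mantel-Haenszel estimate and weights. Replace `commonriskdiff(cl=mh)` with `commonriskdiff(cl=newcombe)`, and name stratified Newcombe limits in the text in place of Wald limits with the Sato variance.
3. State in the report that the main, imputed and stratified HiSCR intervals use different methods, so that small differences between their limits are not over-read.

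The cost is a few lines of code and two SAP sentences. No point estimate changes, and the unstratified and multiple-imputation intervals become slightly narrower on average.
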